6.9.3. Prohibited During the Study

In the event of an emergency, any needed medications may be prescribed without prior approval, but the study medical monitor must be notified of the use of any prohibited medications immediately.

Prohibited Medications Not Requiring Interruption or Discontinuation of Study Treatment

- The following therapies are prohibited during the study until completion of study treatment. Participants receiving any of the following must discontinue such use immediately without interruption or discontinuation of study treatment:
- Low-to-moderate potency TCS (Class VII-IV), calcineurin inhibitors (eg, tacrolimus and pimecrolimus), or crisaborole or high potency TCS (Class III-I) administered for <7 consecutive days. TCS classes (VII-IV) are based on WHO classification of topical corticosteroids^{34,35}). See CRF guidelines.
- Topical antihistamines, tars, topical anesthetics, or antibiotic creams

- Sedating, systemic antihistamines (eg, diphenhydramine, hydroxyzine, promethazine) (nonsedating systemic antihistamines are allowed)
- Initiation of any new (ie, during the screening and treatment period) emollients/moisturizers containing additives such as ceramide, hyaluronic acid, urea, antipruritic or antiseptic agents during the screening and treatment period (patients may continue using stable doses of such emollients/moisturizers if initiated before the screening visit)

Prohibited Medications Requiring Permanent Discontinuation of Study Treatment

Use of the following therapies during the study until completion of study treatment will require permanent discontinuation of study treatment and withdrawal from the study except when specified otherwise below:

- High- to ultra-high potency TCS (Class III-I) administered for ≥7 consecutive days. TCS Classes III-I are based on WHO classification of topical corticosteroids^{34,35}. See CRF guidelines.
- Systemic corticosteroids (intranasal sprays, corticosteroid inhalers, ophthalmic and ear drop corticosteroids are allowed) (requires permanent discontinuation of study treatment but participants are not required to withdraw from the study).
- S1P receptor modulators (eg, fingolimod, ozanimod).
- α4β1 integrin receptor antagonist (eg. natalizumab).
- Anti-CD20 antibodies (eg, rituximab, ocrelizumab), anti-CD52 antibodies (eg, alemtuzumab), other cell depleting therapies (eg, bone marrow transplantation, total body irradiation).

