7. DISCONTINUATION OF STUDY INTERVENTION AND PARTICIPANT DISCONTINUATION/WITHDRAWAL

7.1. Discontinuation of Study Intervention

It may be necessary for a participant to permanently discontinue study intervention. Reasons for permanent discontinuation of study intervention include the following:

- Adverse events noted below (participants with AEs listed below, irrespective of
 causality, will be discontinued from the study intervention) NOTE: Sub bullets below
 are examples and are not intended to be an all-inclusive list.
 - Second episode of confirmed Grade 4 lymphopenia in the same participant (Protocol Sections 10.10.1, 10.10.2)
 - Repeated episode of a serious infection for the same participant (Protocol Section 10.10.2)
 - o Diagnosis of PML (Protocol Section 10.11)
 - Diagnosis of PRES (Protocol Section 8.4.8)
 - ECG changes (Protocol Section 7.1.3)
 - Suspected intolerance associated with first dose cardiac effects (Protocol Section 10.10.3.2)
 - o Malignancy (Protocol Section 8.4.8)
 - o HBV DNA above LLQ (Protocol Section 8.3.7)
 - O Active, latent, or inadequately treated TB infection (Protocol Section 8.3.5)

 PFIZER CONFIDENTIAL

 CT02 GSOP Clinical Protocol Template Phase 1.2.3.4 (01.4 pril 2022)

- o Clinically significant respiratory AE and or a decline in confirmed PFT values (FEV1 and/or FVC below 50% of the predicted values; Protocol Section 10.10.4)
- o Confirmed macular edema (Protocol Section 10.10.5)
- Drug-induced liver injury confirmed cases after all results of reasonable investigations have been received as per Protocol Section 10.5, and alternative etiology have been excluded (Protocol Section 10.10.5)
- Clinically significant safety concern as per investigator's judgement at Week 16 (Protocol Section 7.1.1)
- Death
- Lost to follow up
- Physician decision
- Pregnancy
- Protocol deviation
- Study terminated by Sponsor
- Withdrawal by participant
- Lack of Efficacy

Discontinuation of study intervention does not represent withdrawal from the study. If study intervention is permanently discontinued, the participant should remain in the study to be evaluated for safety. See the SoA for data to be collected at the time of discontinuation of study intervention and follow-up for any further evaluations that need to be completed.

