8.4.8. Adverse Events of Special Interest

AESIs are examined as part of routine safety data review procedures throughout the clinical trial and as part of signal detection processes. They require close monitoring and are assessed as close to real time as possible, and they are promptly reported to the study monitor even if the event is not considered an SAE according to the criteria in Section 10.3.2. Should an aggregate analysis indicate that these prespecified events occur more frequently than expected, eg, based on epidemiological data, literature, or other data, then this will be submitted and reported in accordance with Pfizer's safety reporting requirements. Aggregate analyses of safety data will be performed on a regular basis per internal SOPs.

All AESIs must be reported as an AE or SAE following the procedures described in Sections 8.4.1 through 8.4.4. An AESI is to be recorded as an AE or SAE on the CRF. In addition, an AESI that is also an SAE must be reported using the CT SAE Report Form or via PSSA.

AESI for etrasimod are:

- Cardiovascular events (eg, bradycardia, AV conduction delay and hypertension),
- Macular edema* (Section 10.10.5),
- Pulmonary events (airflow obstruction or decreased gas exchange; Section 10.10.4),
- Infections (severe infections, opportunistic infections, Herpes simplex and Herpes zoster, PML*; Section 10.10.2 and Section 10.11),
- Liver injury (liver transaminase elevation and bilirubin elevation; Section 10.5),
- PRES*,
- Malignancies*

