8.4.10. Medication Errors

Medication errors may result from the administration or consumption of the study intervention by the wrong participant, or at the wrong time, or at the wrong dosage strength.

^{*} A diagnosis of this event requires permanent discontinuation of study intervention. See Section 7.1 for additional AEs requiring discontinuation.

Medication errors are recorded and reported as follows:

Recorded on the Medication Error Page of the CRF	Recorded on the Adverse Event Page of the CRF	Reported on the CT SAE Report Form to Pfizer Safety Within 24 Hours of Awareness
All (regardless of whether associated with an AE)	Any AE or SAE associated with the medication error	Only if associated with an SAE

Medication errors include:

- Medication errors involving participant exposure to the study intervention;
- Potential medication errors or uses outside of what is foreseen in the protocol that do or do not involve the study participant.
- Refer to Section 6.5 for examples of medication error related to compliance with study intervention.

Whether or not the medication error is accompanied by an AE, as determined by the investigator, such medication errors occurring to a study participant are recorded on the medication error page of the CRF, which is a specific version of the AE page and, if applicable, any associated AE(s), serious and nonserious, are recorded on the AE page of the CRF.

In the event of a medication dosing error, the sponsor should be notified within 24 hours.

Medication errors should be reported to Pfizer Safety within 24 hours on a CT SAE Report Form or via PSSA **only when associated with an SAE.**

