10.10.4. Pulmonary Function Monitoring

Based on changes in pulmonary function observed with the use of S1P receptor modulators for relapsing multiple sclerosis^{4,5}, pulmonary function will be assessed in this study.

Participants experiencing clinically significant dyspnea or other respiratory AEs, may need to have additional PFT testing as clinically indicated. Severity of respiratory AEs should be categorized using the CTCAE scale. Investigators should consider interruption of study treatment when there is a clinically significant respiratory AE that leads to limitations in self-care activities of daily living and is associated with PFT decrease. Participants experiencing a confirmed decline in PFT values (FEV1 and/or FVC) below 50% of the predicted values must be discontinued from study treatment and scheduled for a follow-up visit. The decision to interrupt study treatment should be discussed with the blinded Pfizer medical monitor. Participants should be promptly referred to a pulmonologist for further evaluation and treatment. The pulmonologist should be provided with a standard referral letter explaining the reason for the referral along with information about the investigational drug. Clinically significant respiratory AEs should be followed until there is stability, improvement, or resolution.

Reinitiation of study treatment can only be considered if the respiratory AE has improved, stabilized, and/or resolved; the individual risk benefit is favorable (as determined by the Investigator, in agreement with the pulmonologist); and after discussion with the blinded Pfizer medical monitor. The investigator is to ensure first dose cardiac monitoring (Section 10.10.3) is implemented upon drug reinitiation if consecutive days of study treatment are missed as described in Section 7.1.7.

Information regarding the collection of PFTs is provided in Section 8.3.9. PFTs will be performed at timepoints specified in the SoA.

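### Protocol 7.1 makes a clinically significant respiratory AE on its own a permanent stop, while the section it cites, 10.10.4, requires a stop only for confirmed FEV1 and/or FVC below 50% of predicted

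*Protocol*

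**What the plan says.** Protocol Section 7.1 gives reasons for permanent discontinuation. Its AE item covers "participants with AEs listed below, irrespective of" causality, and says that they will be taken off study intervention. A note adds that the sub-entries are examples and not a complete list. The respiratory sub-entry reads "Clinically significant respiratory AE and or a decline in confirmed PFT values (FEV1 and/or FVC below 50% of the predicted values; Protocol Section 10.10.4".

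Section 10.10.4, the section cited there, has three provisions:

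- **Mandatory stop:** "Participants experiencing a confirmed decline in PFT values (FEV1 and/or FVC) below 50% of the predicted values must be discontinued from study treatment".
- **Discretionary interruption:** "Investigators should consider interruption of study treatment when there is a clinically significant respiratory AE that leads to limitations in self-care" activities and is associated with a PFT decrease. The decision to interrupt is to be discussed with the blinded medical monitor.
- **Restart:** "Reinitiation of study treatment can only be considered if the respiratory AE has improved, stabilized, and/or resolved", the individual risk-benefit is favorable in the view of the investigator and the pulmonologist, and the blinded medical monitor has been consulted.

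Section 8.4.8 lists "Pulmonary events (airflow obstruction or decreased gas exchange; Section 10.10.4") as an AESI without the asterisk given to macular edema, PML, PRES and malignancies. The footnote to that list explains the asterisk: "A diagnosis of this event requires permanent discontinuation of study intervention. See Section 7.1 for additional AEs requiring discontinuation".

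Section 6.9.3 makes some therapies a permanent stop in their own right, for example "Systemic corticosteroids (intranasal sprays, corticosteroid inhalers, ophthalmic and ear drop corticosteroids are allowed) (requires permanent discontinuation of study treatment").

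**The concern.** The 7.1 entry and the section it cites give different instructions for the same event. An investigator who works from the 7.1 list would end treatment for good after one clinically significant respiratory AE, even an unrelated one with adequate lung function. An investigator who works from 10.10.4 could continue, or interrupt, evaluate and restart.

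Three things depend on which text is followed:

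- **Treatment of the participant.** Pulmonary events are an AESI, and the risk table in Section 2.3.1 counts clearly defined stopping criteria among the mitigations.
- **A primary safety endpoint.** AEs leading to discontinuation of study treatment are part of the primary safety objective for the Part 1 OLE and for Part 2, where about 340 participants are planned (Protocol Section 3; SAP 3.1). The same event is counted under one text and may not be under the other.
- **The primary efficacy estimand.** Under Estimand E1 (Protocol 9.1.1.1), discontinuation for any reason before the Week 16 visit is non-response. A temporary interruption is not one of E1's two intercurrent events, and Section 6.5 says an interruption on the investigator's judgement under 10.10 is neither a deviation nor a medication error. Under E2 (9.1.1.2), data after discontinuation are treated as missing and imputed; an interruption does not trigger this.

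**Working it through.** **Comparing the rules.** The 50% threshold is the same in both sections, so the question is how the AE and the lung function result combine.

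| Situation | 7.1, reading the conjunction as *or* | 7.1, reading it as *and* | 10.10.4 |
|---|---|---|---|
| Significant respiratory AE, confirmed FEV1 and/or FVC below 50% | Stop | Stop | Stop |
| No significant respiratory AE, confirmed FEV1 and/or FVC below 50% | Stop | No stop from this entry | Stop |
| Significant respiratory AE, FEV1 and FVC at or above 50% | Stop | No stop from this entry | No mandatory stop; consider interruption if self-care is limited and PFT has decreased; conditional restart |

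The *or* reading disagrees with 10.10.4 in the third row and the *and* reading in the second. Neither reproduces the cited section. The note that the entries are examples leaves the list open to additions; it does not soften the instruction for what is listed.

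**Which rule is intended.** Other text points to 10.10.4:

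- Section 7.1.6 treats COVID-19 as a possible reason for temporary discontinuation until recovery.
- Section 10.10.2 requires interruption for a serious infection and allows restart once it resolves; 7.1 itself stops permanently only on a repeated episode. A first serious pneumonia could also be a clinically significant respiratory AE, and the respiratory entry would then override this.
- Pulmonary events carry no asterisk in 8.4.8. This is weaker evidence, because the footnote sends the reader back to 7.1.

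**Which events are affected.** Only the third row, and only where nothing else forces a stop. Systemic corticosteroids end treatment under 6.9.3 whichever text is followed, and before Week 16 they count as prohibited medication under E1. An event managed with inhaled therapy is in scope, since corticosteroid inhalers are allowed.

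The third row can occur. Exclusion criterion 12 requires FEV1 and FVC of at least 70% of predicted at screening. A 20% relative fall, the size that prompts a repeat test in 8.3.9, takes the lowest eligible value to 0.70 × 0.80 = 56% of predicted, still above 50%.

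**Size for the primary estimate.** Inputs from Protocol 9.5: 30 per group, assumed response 39% on etrasimod and 9% on placebo.

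- Planned half-width: 1.96 × √(0.39 × 0.61/30 + 0.09 × 0.91/30) = 1.96 × √(0.00793 + 0.00273) = 1.96 × 0.1033 = 0.202, or 20.2 points, as the protocol states.
- One participant who would have responded but is stopped permanently before Week 16: 1/30 = 0.033, or 3.3 points off that arm's rate.
- Ratio: 3.3/20.2 = 0.16, about one sixth of the half-width.
- The effect is zero for a participant who would not have responded, or who receives systemic corticosteroids.

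The documents give no rate for these events, so no expected count is calculated.

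**The case against.** The strongest reply is that the 7.1 list is an index and the cited section governs. The ECG entry works that way: it names only ECG changes and points to 7.1.3, which interrupts for confirmed QTc above 500 ms, allows a conditional restart and stops permanently on recurrence. Nobody would read that entry as stopping treatment for any ECG change. This stands as evidence of intent. It does not remove the defect, because the respiratory entry is not a bare label. It states its own trigger, and that trigger differs from the one in the section it cites.

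The second reply is that the practical consequence is limited. This stands. A reader might infer that sites would re-expose participants without coordination. The documents do not support that: interruption is to be discussed with the blinded medical monitor, and restart needs the pulmonologist's agreement and a further discussion with the monitor. Physician decision is also a listed reason for permanent discontinuation, so an investigator may stop after such an AE under either text.

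The third reply is that E1 is barely touched. This also stands. An effect needs a significant respiratory AE before Week 16, FEV1 and FVC at or above 50% of predicted, no other mandatory stop, a site that follows 7.1 literally, and a participant who would otherwise have responded. Part 1 is an estimation study without hypotheses (9.1), and SAP Table 4 shows non-responders by arm and reason for discontinuation, so AE-related stops would be visible.

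**Conclusion.** The inconsistency is real and should be corrected. The stopping rule for this AESI is misstated in 7.1, and no reading of its conjunction matches the section it cites. The weight of the text favors 10.10.4 as the intended rule, so this is a drafting error in 7.1, not a contest between two equally supported policies.

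The main consequences are an unnecessary permanent stop for individual participants and inconsistent counting of AEs leading to discontinuation. The efficacy consequence is secondary: at most 3.3 points in one arm per reclassified responder, assuming the planned 30 per group.

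A reader might go further and infer material bias in the primary estimate, or derive an event count from the 40.3% asthma prevalence quoted in Section 2.2. Neither is supported. That figure is a comorbidity prevalence in one sample, not a rate of clinically significant respiratory AEs on treatment, and nothing in the documents converts one into the other.

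**What to change.** Reword the respiratory entry in Section 7.1 to:

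> Confirmed decline in FEV1 and/or FVC below 50% of predicted, or a clinically significant respiratory AE for which study treatment has been interrupted and, after evaluation, cannot be reinitiated under Section 10.10.4.

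Two features of this wording matter. It applies only after an interruption, so it does not reach participants whose treatment was never withheld. It also turns on the outcome of evaluation. A rule that stopped treatment whenever the restart conditions were unmet would usually apply at the onset of the AE and recreate the conflict.

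Making 10.10.4 as strict as 7.1 is not recommended, because it would clash with 7.1.6 and 10.10.2.

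The cost is one list entry in a protocol amendment, with no new procedure or data collection. The same amendment can correct a clerical slip: the closing cross-reference of the drug-induced liver injury entry in 7.1 points to 10.10.5 (ophthalmic monitoring) and should be 10.5.

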 - b. History of second degree or third-degree atrioventricular block, sick sinus syndrome or periods of asystole for > 3 seconds without a functional pacemaker
 - c. History of recurrent symptomatic bradycardia or recurrent cardiogenic syncope
 - d. Screening or Day 1 predose vital signs (taken in the sitting position) with a HR
 50 bpm OR systolic blood pressure (BP) < 90 mm Hg OR diastolic BP
 55 mm Hg. Abnormal vital signs should be confirmed by 1 repeat measurement.

Abnormal results that are confirmed on a repeat assessment are considered exclusionary.

- e. Screening or Day 1 predose electrocardiogram (ECG) with PR interval \geq 200 ms or QTcF \geq 450 ms in males or \geq 470 ms in females
- f. Start, stop, change dosage of any Class I to IV anti-arrhythmic drugs within 1 week before Day 1

Other Exclusion Criteria:

14. Investigator site staff directly involved in the conduct of the study and their family members, site staff otherwise supervised by the investigator, and sponsor and sponsor delegate employees directly involved in the conduct of the study and their family members.

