6.5. Study Intervention Compliance

When participants self-administer study intervention(s) at home, compliance with study intervention will be assessed at each visit through a combination of the accounting of unused study intervention returned by the participant at the study visits and discussion (direct questioning) with the participant which will be documented in the source documents and CRF. Deviation(s) from the prescribed dosage regimen should be recorded in the CRF.

A record of the number of tablets dispensed to and taken by each participant must be maintained and reconciled with study intervention and compliance records. Intervention start and stop dates, including dates for intervention delays, will also be recorded in the CRF.

Part 1: The Week 16 visit is the first dose of open label (etrasimod) treatment. Sites must contact participants 1-2 business days prior to the Week 16 visit to remind them not to take study intervention on the day of the Week 16 visit. Should the participant come to the site having already taken study intervention, all Week 16 procedures will be completed, except for administering open label treatment and first-dose cardiac monitoring procedures for which an unplanned visit is required as soon as possible (within 3 days). The unplanned visit should be scheduled in the morning and not on a Friday or day before a site-observed holiday. The participant will continue taking blinded study intervention up to 1 day prior to the unplanned visit. Again, sites must contact the participants 1-2 business days prior to the unplanned visit to remind them not to take study intervention the day of the visit. The unplanned visit will be the start of the OLE period. See Section 10.10.3 for details of first-dose cardiac monitoring procedures.

The following non-compliance cases will be considered **medication errors** and will be discussed with the sponsor for possible withdrawal from the study:

- 1. Participants interrupting study intervention for ≥ 2 consecutive days within the first week of treatment or Week 16 of Part 1, or for ≥ 7 consecutive days after the first week of treatment (excluding Week 16 of Part 1 where missing 2 doses applies).
 - NOTE The first-dose cardiac monitoring outlined in Section 10.10.3 must be performed any time a participant reinitiates study treatment following dose interruptions as described above and the participant must take the next dose of study treatment at the study site.

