6.8. Treatment of Overdose

The following scenarios are considered overdose:

- Consuming >3 mg on Day 1, on Week 16 visit day in Part 1, or on a day of treatment re-initiation after protocol defined treatment interruptions.
- Consuming >5 mg any day after Day 1 or starting a day after Week 16 visit in Part 1 except on a day of treatment re-initiation, as specified above.

There is no specific treatment recommended for an overdose but to provide supportive care if clinically indicated. AV conduction delays and bradycardia were observed on Day 1 in several participants who received 5 mg etrasimod in Phase 1 single-ascending dose Study (Arena Study APD334-001); this dose was not used in subsequent clinical studies. Etrasimod has not been evaluated for drug abuse or dependence. Participants with suspected overdose will be counseled on correct dosing and administration of study treatment.

In the event of an overdose, the investigator should:

- 1. Contact the study medical monitor within 24 hours.
- 2. Closely monitor the participant for any AEs/SAEs and laboratory abnormalities as medically appropriate and follow up until resolution, stabilization, the event is otherwise explained, or the participant is lost to follow-up (as defined in Section 7.3).
- 3. Document the quantity of the excess dose as well as the duration of the overdose in the CRF.
- 4. Overdose is reportable to Pfizer Safety only when associated with an SAE.

Decisions regarding dose interruptions or permanent discontinuation will be made by the investigator in consultation with the study medical monitor as needed based on the clinical evaluation of the participant.

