In the event of discontinuation of study intervention, it must be documented on the appropriate CRF/in the medical records whether the participant is discontinuing further receipt of study intervention or also from study procedures, further study follow-up, and/or future collection of additional information.

7.1.1. Discontinuation after Part 1 DB (Week 16) due to a Clinically Significant Safety Concern

Per investigator's judgement, participants must permanently discontinue study intervention at the Part 1 Week 16 visit if they experienced an AE and/or SAE during the DB study portion that was a clinically significant safety concern for study continuation which may or may not have resulted in study treatment interruption. The investigator may seek medical monitor's consideration, if needed, to determine participant continuation.

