7.1.7. Temporary Discontinuation

Dose interruptions are defined as the following consecutive days of missed study treatment:

- \geq 2 consecutive days within the first week of treatment or during Week 16 of Part 1, or
- ≥7 consecutive days after the first week of treatment (excluding Week 16 of Part 1 where missing 2 doses applies)

If the Investigator deems it necessary to withhold study treatment due to an adverse event, temporary withholding is permitted for up to 6 days (after the first week of treatment) without obtaining prior approval from the study medical monitor. Planned dose interruptions during the first week of treatment requires consultation with the study medical monitor. If study treatment interruption ≥ 7 days is required for a medical reason at any time in the study, the Investigator must contact the study medical monitor for further instruction as soon as this is anticipated. Any time a participant reinitiates study treatment following protocol-defined dose interruptions, the first dose cardiac monitoring outlined in Section 10.10.3 must be performed and the participant must take the next dose of study treatment at the study site.

Doses not taken due to an adverse event per investigator's request do not constitute protocol deviations or medication errors and should not be considered dosing errors but should be noted in the dosing log with the reason for reduced drug consumption clearly described.

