8.3.3.1. Alternative Facilities for Electrocardiograms

If the participant is unable to visit the study site for ECGs, the participant may visit an alternative certified facility to have the ECGs performed. Use of alternative facilities for ECGs is not permitted on Day 1 (and Day 2, if applicable), Week 16 of Part 1 (and a day after, if extended cardiac monitoring is applicable), or for cardiac monitoring during treatment re-initiation after protocol pre-defined treatment interruptions (see Section 7.1.6). Qualified study site personnel must order, receive, and review results.

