10.10.3. First-Dose Cardiac Monitoring

Cardiac monitoring following treatment initiation applies to the first dose administered in the Treatment Period (Day 1). Day 1 predose (ie, Baseline) vital signs (resting HR, BP, body temperature, and respiratory rate) will be used as the baseline measurements. The lowest predose HR measurement (by vital signs) will be used for comparison to the postdose measurement. It should be noted that in this section heart rate refers to pulse rate. Pulse rate will be collected as part of vital signs and heart rate will be collected as part of the ECG.

Cardiac monitoring is required at the Day 1 (first blinded dose) of Part 1 and Part 2 and Week 16 (first open label etrasimod dose) of Part 1 and will also be necessary to reinitiate study treatment if consecutive days of study treatment are missed as described in Section 7.1.7. These visits for cardiac monitoring should be conducted in the morning and not on a Friday or the day before a site-observed holiday. In the following sections describing first-dose cardiac monitoring, Day 1 refers to the first day of treatment in the Treatment Period, but the same procedures will also be used at the Week 16 visit in Part 1 (first open label dose) and the first day of treatment re-initiation following the defined periods of treatment interruption noted above. Day 2 refers to the subsequent dosing day.

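### Week 16 is the first etrasimod dose for former placebo participants, but the Day 1 numeric pre-dose limits on HR, BP, PR and QTcF are not repeated there

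*Protocol*

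**What the plan says.** Protocol Section 6.5 states: "The Week 16 visit is the first dose of open label (etrasimod) treatment". For anyone randomized to placebo it is the first exposure to the drug. The protocol otherwise handles the visit as a second Day 1:

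- Cardiac monitoring (10.10.3): "the same procedures will also be used at the Week 16 visit in Part 1 (first open label dose"; the discharge criteria in 10.10.3.1.1 name the visit as well.
- Overdose (6.8): the stricter limit of more than 3 mg applies "on Day 1, on Week 16 visit day in Part 1, or on a day of treatment re-initiation".
- Missed doses (7.1.7): an interruption is two or more "consecutive days within the first week of treatment or during Week 16 of Part 1".
- ECG location (8.3.3.1): outside facilities are barred on Day 1 and at "Week 16 of Part 1 (and a day after, if extended cardiac monitoring is applicable").

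The Part 1 schedule of activities places vital signs and a 12-lead ECG before the Week 16 dose.

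The numeric limits sit in Section 5.2. Criterion 13d covers HR below 50 bpm, SBP below 90 mm Hg and DBP below 55 mm Hg: "Abnormal results that are confirmed on a repeat assessment are considered exclusionary". Criterion 13e covers PR of 200 ms or more, and QTcF of 450 ms or more (males) or 470 ms or more (females). Both are tied to Screening and Day 1 pre-dose. Section 8.3.3 repeats the ECG limits for those visits and refers all others to Sections 7.1.3 and 10.7.

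The Week 16 gate is Section 7.1.1. Participants must stop "at the Part 1 Week 16 visit if they experienced an AE and/or SAE during the DB study portion" that the investigator regards as a clinically significant safety concern. On the monitor it says: "The investigator may seek medical monitor's consideration, if needed, to determine participant continuation".

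**The concern.** Section 2.3.1 relies on two protections against first-dose cardiac effects: keeping out participants at elevated cardiac risk, and monitoring for four hours after the dose. At Week 16 the second is repeated in full and the numeric part of the first is not. Section 8.4.6 names the expected effects as heart-rate reduction and transient AV conduction delay, so HR and PR matter most. BP and QTcF belong to the same Day 1 limits.

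Monitoring, discharge and stopping rules act only once the tablet has been swallowed. A value that would have kept someone from the first dose on Day 1 can therefore be followed by a first dose at Week 16 on the investigator's judgement alone. Participant safety is at stake. The Week 16 efficacy assessments are made before dosing, so no estimand or efficacy result is affected.

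**Working it through.** There is no plan figure to reproduce. The check sets the Day 1 limits beside every rule that could govern the same measurement before the Week 16 dose.

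**Who is exposed.** Section 9.5: 60 randomized 1:1, so 60/2 = 30 on placebo, fewer after dropout.

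**What applies to each measurement.**

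| Measurement | Day 1 limit (5.2) | Required pre-dose action at Week 16 | Listed in 10.7 |
|---|---|---|---|
| HR | <50 bpm, confirmed | none | sinus bradycardia <40 bpm; symptomatic bradycardia, any rate |
| SBP / DBP | <90 / <55 mm Hg, confirmed | none | not covered (ECG list) |
| PR | ≥200 ms | none | new PR >280 ms |
| QTcF, males | ≥450 ms | none until confirmed new-onset QTc >500 ms (7.1.3) | >480 ms, or rise ≥60 ms |
| QTcF, females | ≥470 ms | as for males | as for males |

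Section 10.7 describes findings that may or do count as AEs or SAEs, and recommends them as core-laboratory alerts. It attaches no dosing hold and no timing relative to the dose.

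**Width of the ranges that barred dosing on Day 1 but require no action at Week 16.**
- HR: 40 to 49 bpm is not listed by rate (50 − 40 = 10 bpm); below 40 bpm is listed only.
- PR: 280 − 200 = 80 ms not listed; above 280 ms listed only.
- QTcF, males: 480 − 450 = 30 ms with no absolute-value listing, then 500 − 480 = 20 ms listed only.
- QTcF, females: 480 − 470 = 10 ms, then 500 − 480 = 20 ms listed only.

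**Does the eligibility wording import the limits?** The synopsis and schedule of activities ask that participants remain eligible at Week 16. The schedule refers this to 7.1.1, which has no values; Section 4.1 omits the phrase; 13d-e name Screening and Day 1; and 8.3.3 sends other visits elsewhere. The limits are not carried over.

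**Comparison within the protocol.** Under 7.1.3, restarting after a QTc >500 ms interruption requires QTcF below 450 ms (males) or 470 ms (females), cardiologist confirmation that the drug was not the cause, a favourable risk-benefit view, and discussion with the medical monitor. The first-ever dose at Week 16 has neither the QTcF limit nor the required discussion.

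**Do post-dose rules fill the gap?** Not fully. A PR of 260 ms passes the ECG discharge criterion, which fails only at second-degree AV block or higher. The HR criterion accepts a value below 50 bpm if the fall from baseline is under 10 bpm. If the Week 16 pre-dose value is the comparator (implied by 10.10.3 but not stated), a pre-dose 44 bpm could pass at 44 − 9 = 35 bpm, other criteria being met.

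**Timing.** Part 1 schedules no ECG between Day 1 and Week 16: 113 − 1 = 112 days, or 107 to 117 with the ±5-day window. The Week 16 ECG is thus the first scheduled chance to see a change in PR or QTcF. HR and BP are also measured at Weeks 4, 8 and 12.

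**The case against.** A reader might infer that nothing stands between an abnormal Week 16 reading and the dose. The documents do not support that. The ECG and vital signs are taken first. Section 8.3.3 has the investigator classify each ECG as normal, abnormal but insignificant, or abnormal and significant. The last paragraph of 7.1.3 requires a decision on whether a participant with a clinically significant finding can continue, with the review of the printed ECG documented. A new clinically relevant finding should be reported as an AE, which can feed 7.1.1. Nor is it right that HR of 40 to 49 bpm escapes all notice: 10.7 lists symptomatic bradycardia with no rate limit among possible SAEs.

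A reader might also infer that no second pair of eyes exists. ECGs go to a central reader, 10.7 alerts go to the study team, to which the blinded monitor belongs, and Section 10.10 names that monitor as the contact for questions on OLE roll-over. What remains of the concern is that no text requires any of these to be completed before the dose, and roll-over contact depends on the investigator having a question.

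The sponsor can add that this is deliberate. The current amendment's summary of changes says Week 16 continuation rests on investigator judgement with optional consultation, and that 8.3.3 was expanded to stress the Screening and Day 1 values. That stands as a reason to leave the decision with the investigator. It does not explain why the first exposure has a lighter rule than a restart. The sponsor can also say that these participants passed the limits at Screening and Day 1, and that 6.9.3 restricts anti-arrhythmic changes within one week of initiation. Both lower the likely number affected; neither sets a limit on a Week 16 reading.

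**Conclusion.** The gap is real and narrow. Safeguards exist before the Week 16 dose, but they rest on judgement. Below a confirmed new-onset QTc above 500 ms, no HR, BP, PR or QTcF value triggers a required hold or a required monitor contact before what is, for up to about 30 participants, the first exposure. It should be fixed as an inexpensive safety improvement.

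The number who would fall in the affected ranges cannot be derived from the documents, and no claim of expected harm is made. The conclusion rests on reading the remain-eligible wording as pointing to 7.1.1, and on 8.3.3 being complete when it names 7.1.3 and 10.7 for other visits. It concerns HR, BP and ECG intervals only; other findings, such as a positive pregnancy test or Grade 4 lymphopenia, have their own hold or stop rules.

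**What to change.** Add to Sections 7.1.1 and 8.3.3, and cross-refer from the schedule-of-activities row *Assess treatment continuation criteria*:

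> Before the first open-label dose at Week 16, in both arms, any of the following requires documented discussion with the blinded study medical monitor before dosing: HR <50 bpm, SBP <90 mm Hg or DBP <55 mm Hg, each confirmed on one repeat; PR ≥200 ms; or QTcF ≥450 ms (males) / ≥470 ms (females) on the on-site ECG. The investigator makes the final decision. Section 7.1.3 is unchanged for QTc >500 ms.

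This is a required contact, not a bar to dosing, so the same value may still be dosed, but only after a recorded second opinion. Applying it to both arms protects the blind.

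The cost is amendment wording, one source or CRF item and occasional same-day calls. The measurements are already scheduled, the on-site machine reports PR and QTcF, and repeat vital signs are already allowed during first-dose monitoring. The downside is some short dosing delays, including for etrasimod-arm participants who already tolerate the drug.
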